3.9. Withdrawals, Dropouts, Loss to Follow-up

Randomized subjects who are withdrawn or discontinue from the study will not be replaced.

3.10. Missing, Unused, and Spurious Data

Every effort will be made to collect all data at specified times.

For the efficacy response outcomes, subjects with missing response data are considered to have an indeterminate response unless the subject was a determined to be a failure at an earlier timepoint. Subjects with an indeterminate response are included in the denominator of the success/cure rate calculation and thus, are treated in the same manner as failures in the analysis.

If the start time for a non-study medication starting on same day of treatment start is missing, the medication will be considered concomitant. If the start time for an adverse event starting on same day of treatment start is missing, the adverse event will be considered treatment-emergent. If start and end dates are missing entirely the event will be considered treatment-emergent.

In general, there will be no substitutions made to accommodate missing data points. All data recorded on the eCRF will be included in data listings that will accompany the CSR.

3.11. Visit Windows

Study procedures should be completed within the windows provided in the Schedule of Assessments and Procedures in Table 1-1. Visit windows for each evaluation are specified in Table 3-2.

CONFIDENTIAL Page 31 of 56

Table 3-2: Visit Windows

Evaluation	Protocol-Specified Interval	Efficacy Analysis Window
Screening	Study Day -2 to Study Day 1	Study Day -2 to Study Day 1
Baseline	Study Day 1 (last measurement prior to the administration of the first dose of study drug)	Study Day 1 (last measurement prior to the administration of the first dose of study drug)
Day 5	Study Day 5 to Study Day 9	Study Day 5 to Study Day 9
Day 14 (±1 day)	Study Day 13 to Study Day 15	Study Day 13 to Study Day 21, unless study drug was terminated prior to Day 13 and had the efficacy assessment on EOT. If study drug was stopped early because the PI thought the subject was a clinical cure, the subject must be assessed during the Day 14 window.
Day 28 (±2 day)	Study Day 26 to Study Day 30 (for IC subjects)	Study Day 26 to Study Day 30 (for IC subjects)
Follow-up	Study Day 45 to Study Day 52 (Study Day 52 to Study Day 59 for IC subjects)	Study Day 38 to Study Day 59 (Study Day 45 to Study Day 66 for IC subjects)

For summaries of safety, including vital signs, 12-lead ECGs, and clinical laboratory parameters, summaries will be provided by Study Day (as appropriate) while on therapy, at the EOT and FU visits. If more than 1 measurement is available within the EOT visit window (+2 days after last dose of study drug), the measurement taken closest to last dose of study drug will be used. If more than 1 measurement is available within the FU visit (Days 45-52; Days 52-59 for IC subjects), the measurement taken on the nominal visit will be used. If no nominal FU visit is available, the earliest measurement in the window will be used.

3.12. Interim Analyses

To demonstrate preliminary efficacy and safety of CD101, an interim analysis will be performed after approximately 50-70 subjects in the mITT population have been enrolled in Part A, completed study drug therapy, and the data are deemed clean. Several steps will be implemented to help avoid bias including: the analysis will be performed by an unblinded statistician who is not involved in the day to day statistical and data management aspects of the study, the tables will provide summary data by treatment group assignment but the group assignment of each individual subject will remain blinded until the completion of the study, and only a few key efficacy and safety tables will be provided.

This unblinded interim analysis will consist of the 5 efficacy and safety tables listed below:

- Table 14.2.1.1 Overall Response at Day 14 (mITT Population)
- Table 14.2.4.1 Investigator's Assessment of Clinical Response at Day 14 and Follow-up (mITT Population)
- Table 14.3.1.1 Summary of Treatment-Emergent Adverse Events (Safety Population)
- Table 14.3.1.3 Treatment-Emergent Adverse Events by System Organ Class, Preferred Term and Maximum Severity (Safety Population)
- Table 14.3.3.3 Post-Baseline Shifts of >=2 Toxicity Grades for Laboratory Parameters (Safety Population)

CONFIDENTIAL Page 32 of 56

Guidelines for determining continuation of Part B following the interim analysis will be provided in a note-to-file memo and will be utilized by the unblinded analysis team. The determination of whether or not to continue Part B as described in the protocol will be made by the unblinded analysis team and the recommendation will be forwarded on to Sponsor. If any of the 'stopping criteria' outlined in the memo are met, the medical team and statistician will be unblinded for the 5 tables only, and determine if it is safe to proceed to Part B.

3.13. Timing of Part A and Part B Analyses

Once Part A is completed, the database for Part A will be locked and a full unblinded analysis with all summary tables will be performed on Part A alone. Individual subject data will only be made available to the Sponsor if needed to better understand the efficacy and safety of CD101.

The data from Part B will only be unblinded and analyzed after database lock for Part B at completion of the study.

All analyses will be completed for Part A. Selected analyses will be completed only for Part B and for Parts A and B combined.

CONFIDENTIAL Page 33 of 56

4. PATHOGEN DETERMINATION

Fungal pathogen determination from blood specimens is based on the genus and species identification of isolates. If the genus identification is the same between the local and central mycology laboratory but the species identification is discrepant, the central laboratory identification will be used. If the local laboratory grows an isolate but the central laboratory is not able to grow the isolate, if isolates were lost during transportation or storage, or there are major discrepancies between the local and central laboratory in the identification of species, the central laboratory will request the local laboratory to resend the isolate. If the central laboratory identification is not available for an isolate, the local laboratory identification will be used. For any remaining major discrepancies in species identification between the central and local laboratory, the central laboratory identification will be used as the default identification. This procedure will be followed for identification of fungal pathogens at baseline and any post-baseline time points.

Any *Candida* species isolated from blood cultures or normally sterile sites will be considered pathogens in this study. Fungal isolates other than *Candida* and bacterial isolates from blood cultures will not be considered pathogens for this study.

CONFIDENTIAL Page 34 of 56

5. STATISTICAL ANALYSIS

5.1. Study Population

All analyses describing the study population (Section 5.1.1 through Section 5.1.7) will be conducted separately for Parts A and B unless otherwise noted.

5.1.1. Analysis Populations and Subject Disposition

Each subject providing informed consent in the study will be accounted for. The number and percentage of subjects in each of the analysis populations will be summarized overall and by treatment group. The reason(s) for exclusion from the mITT population will be summarized and a corresponding listing for the ITT population will be provided showing each subject's inclusion in or exclusion from the Safety and mITT populations and reason(s) for exclusion. The number and percentage of subjects prematurely withdrawing from the study and the primary reason for premature withdrawal will be summarized by treatment group for the ITT population as will the number and percentage of subjects prematurely discontinuing study drug regimen and the primary reason for premature discontinuation. A separate listing will be provided for those subjects who sign informed consent but are not randomized (screen failures), including their specific reason for exclusion. The number and percentage of randomized subjects identified as failing to meet at least 1 inclusion criterion or meeting at least 1 exclusion criterion, and the specific inclusion criterion not met/exclusion criterion met, will be summarized by treatment group and overall, for the ITT population. A supportive by-subject listing will be generated for all inclusion criterion not met and exclusion criterion met.

5 1 2 Protocol Deviations

A by-subject listing of all protocol deviations, with a flag for minor and major deviations by treatment group will be produced.

5.1.3. Demographics and Baseline Characteristics

Demographic information including sex, females of child-bearing potential, race, ethnicity, age, age category (<65 years versus \geq 65 years), diagnosis (candidemia and/or IC), height, weight, body mass index (BMI), estimated creatinine clearance (based on Cockcroft-Gault formula), Child-Pugh score category for those subjects with a history of chronic cirrhosis (<7 and 7-9) and APACHE II score category (<10, 10-19, and \geq 20) will be summarized by treatment group and overall for each study population. Age will be calculated and entered into the eCRF by the site and will be based on the date of informed consent (date of informed consent minus the date of birth, in years). BMI (kg/m²), calculated by dividing weight (kg) by height (m²) will be captured in the eCRF.

The Cockcroft-Gault formula for estimated creatinine clearance (eCrCl) is:

$$eCrCl = \frac{140 - [Age(years)] \times [Body\ Mass\ (kg)] \times [0.85\ if\ Female]}{72 \times [Serum\ Creatinine\ (mg\ /\ dL)]}$$

Demographic summaries by treatment group will also be presented for the ITT population in the geographic region, hepatic insufficiency, renal function status, and renal disease subgroups defined in Section 3.8. By-subject listings for all demographics and baseline characteristics will also be provided.

CONFIDENTIAL Page 35 of 56

5.1.4. Medical and Surgical History

Medical and surgical history, including procedures recorded at screening will be summarized by treatment group, system organ class (SOC), and preferred term (PT) using version 19.0 of MedDRA in the Safety population. For these summaries, subjects with more than 1 medical/surgical history within the same SOC or PT will be counted only once for that SOC or PT.

5.1.5. *Candida* Risk Factors

Analyses of *Candida* risk factors will be completed for Part A and for combined Parts A and B.

The number and percentage of subjects with each of the following risk factors at Screening will be summarized by treatment group in the mITT population: central vascular catheter (CVC), active malignancy, use of broad-spectrum antibiotic therapy, diabetes mellitus, immunosuppression, major surgery, total parenteral nutrition, transplant recipient (solid organ, bone marrow), trauma, dialysis, burns, pancreatitis, and admission to the Intensive Care Unit (ICU). For subjects admitted to the ICU, descriptive statistics for the length of time in days will be summarized. For subjects who had a catheter, a summary of the number and percentage of subjects by type of catheter will also be provided. Descriptive statistics for the longest duration of catheter placement by type of catheter for each subject at screening will also be provided. The number and percent of subjects who had their catheter removed within 48 hours after diagnosis with candidemia and subjects who did not have their catheter withdrawn will be summarized by treatment group in the mITT population.

5.1.6. Systemic Signs of Candidemia and/or IC at Baseline

The number and percentage of subjects with systemic signs at baseline determined to be attributed to candidemia and/or IC by the PI will be summarized by treatment group for subjects in the mITT population. Signs include fever, hypothermia, hypotension, tachycardia, and tachypnea. A by-subject listing of systemic signs and symptoms assessed at baseline, Day 5 (signs only), Day 14 (±1), Day 28 (±2 for IC subjects) and the FU visit, including the other clinical signs and symptoms reported on the eCRFs, and the PI determination of whether or not the sign/ symptom is attributable to candidemia will also be provided.

5.1.7. Baseline Fungal Pathogens

The genus and species of fungal pathogens identified from baseline blood cultures and normally sterile sites will be summarized by treatment group for subjects in the mITT population.

For each baseline *Candida* species, a summary of the distribution of minimum inhibitory concentration (MIC) results from the central lab (or if not available, from the local lab) will be presented both by treatment group and for treatment groups combined for subjects in the mITT population in separate tables for each of CD101, caspofungin, anidulafungin, micafungin, and fluconazole. In addition, for each baseline *Candida* species, the MIC₅₀, MIC₉₀, and MIC_{Range} for CD101, caspofungin, and fluconazole will be summarized, only where there are at least 10 of a particular *Candida* species with susceptibility data available from the central mycology laboratory in each treatment group, will be summarized both by treatment group and for treatment groups combined for subjects in the mITT population.

A by-subject listing will be provided displaying all MIC results for any baseline *Candida* species that is resistant to echinocandins; a separate by-subject listing will be provided displaying all MIC results for any baseline *Candida* species that is resistant to fluconazole.

CONFIDENTIAL Page 36 of 56

5.2. Extent of Exposure and Concomitant Procedures

Analyses of study drug exposure will be conducted for Part A, Part B, and Parts A and B combined. Analyses of prior and concomitant medications and procedures will be conducted separately for Parts A and B.

5.2.1. Study Drug Exposure

Descriptive statistics for the duration of study drug therapy (IV and oral) will be summarized by treatment group for the Safety and mITT populations. Treatment duration is defined as the date of the last dose of study drug - first dose of study drug +1 day. The number and percentage of subjects with 1–7, 8-14, 15-21 and >21 days of exposure (IV and oral) as defined above will be presented. Descriptive statistics will also be provided separately for the duration of IV therapy and the duration of oral therapy. The number and percentage of subjects with 1-3, 4-7, 8-14 and 15-21 days of IV therapy will be presented. Additionally, the study drug exposure summaries by treatment group will be presented for the Safety population in the geographic region, hepatic insufficiency, renal function status, and renal disease subgroups defined in Section 3.8.

The number and percentage of subjects switching to oral study drug therapy and a frequency distribution of the day of oral switch will be summarized by treatment group for the Safety and mITT populations. A by subject listing of all IV doses over time and a separate by-subject listing of the start and stop dates for oral therapy will be provided.

Analyses of study drug exposure in mITT population will only be conducted in Parts A and B combined

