Subjects randomized to the CD101 IV treatment group 1 will receive 1 dose of CD101 IV (400 mg) over 60 (±10) minutes on Day 1 and Day 8 and IV placebo on other study days in order to maintain the blind; subjects who require >14 days of IV therapy will receive an optional third dose of CD101 IV (400 mg) on Day 15. Subjects with IC are allowed an optional CD101 IV dose (400 mg) on Day 22 if additional therapy is required. Subjects in group 1 will receive IV placebo on other study days in order to maintain the blind. Subjects randomized to the CD101 IV treatment group 2 will receive 1 dose of CD101 IV (400 mg) over 60 (\pm 10) minutes on Day 1, 200 mg on Day 8 and IV placebo on other study days in order to maintain the blind; subjects who require >14 days of IV therapy will receive an optional third dose of CD101 IV (200 mg) on Day 15. Subjects with IC are allowed an optional CD101 IV dose (200 mg) on Day 22 if additional therapy is required. Subjects in group 2 will receive IV placebo on other study days in order to maintain the blind. Subjects may receive oral step-down therapy after ≥3 days of IV therapy, if criteria are met. Step-down therapy in both CD101 IV treatment groups will be oral placebo, in order to maintain the blind. Subjects who have already switched to oral step-down therapy will receive both oral placebo and CD101 IV on Day 8 and optional oral placebo and CD101 IV on Day 15 for subjects who require >14 days of therapy. Dosage adjustments are not allowed. Intravenous study drug is administered 24 (±2) hours after study drug was administered on the previous day.

Subjects randomized to the caspofungin group will receive IV caspofungin (70 mg loading dose on Day 1 and then 50 mg/day) for ≥ 3 days up to a maximum of 21 days for subjects with candidemia only or up to a maximum of 28 days for subjects with IC. After ≥ 3 days of IV therapy, subjects in the IV caspofungin group can be switched to oral step-down therapy if criteria are met. Step-down therapy in the caspofungin treatment group will be oral fluconazole (a loading dose of 800 mg [4 capsules] on the first day followed by 400 mg [2 capsules]/day thereafter). In order to maintain the blind, subjects who have already switched to oral step-down therapy will receive both oral fluconazole and IV placebo on Day 8, Day 15 for subjects who require ≥ 14 days of therapy. Intravenous study drug is administered 24 (± 2) hours after study drug was administered on the previous day.

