APACHE = Acute Physiology and Chronic Health Evaluation; ECG = electrocardiogram; EOT = End-of-Therapy; ESCMID = European Society Clinical Microbiology and Infectious Disease; FU = follow-up; IC = Invasive Candiasis; IDSA = Infectious Disease Society of America; IV=Intravenous; IVD = in vitro diagnostic; PK = pharmacokinetic.

- a. Study Day 1 is the first day of study drug administration; subsequent study days are consecutive calendar days.
- b. The time windows on Study Day 8, 14, 15, 22, and 28 visits apply only to subjects already stepped down to oral therapy and discharged from the study site.
- c. Perform if further therapy is clinically indicated; only for subjects with IC (with or without candidemia). Subjects will be considered to have IC if there is a positive culture for *Candida* spp. from a normally sterile site other than blood or if there is a positive sponsor-approved rapid IVD or blood culture for *Candida* spp. combined with radiographic evidence of IC.
- d. The Day 28 visit is only for subjects with IC (with or without candidemia). Note that the Day 28 (±2 days) visit could be the same visit as the EOT visit if the subject receives ≥26 days of therapy.
- e. Written informed consent must be obtained prior to initiating any study related assessments or procedures.
- f. Medical history for the last 5 years and *Candida* risk factors for the last 3 months (eg, central line, active malignancy, broad-spectrum antibiotic therapy, diabetes mellitus, immunosuppression, major surgery, total parenteral nutrition, transplant recipient, trauma, dialysis, burns, pancreatitis) and Intensive Care Unit admission and discharge (if applicable). Short-term central venous catheters (eg, peripherally-inserted central catheters, internal jugular or subclavian central venous catheters) and long-term central venous catheters (eg, tunneled catheters) are recommended to be removed within 48 hours after diagnosis with candidemia, consistent with IDSA and ESCMID guidelines
- g. Physical exams are required at Screening, on Day 14, Day 28 (±2 days; only for subjects with IC), and at the FU visit. Height is recorded at Screening. Weight is recorded at Screening, on Day 14, and at the FU visit. If a physical exam is performed at any other visit, abnormal findings that represent a new or worsening condition as compared to baseline should be recorded as an adverse event.
- h. Calculate Child-Pugh score only if the subject has a history of chronic cirrhosis

CONFIDENTIAL

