- u. On Day 8, subjects will receive either IV CD101 (if in a CD101 group and not switched to oral therapy); IV caspofungin (if in caspofungin group and not switched to oral therapy), IV CD101 plus oral placebo (if in a CD101 group and already switched to oral therapy); or IV placebo plus oral fluconazole (if in caspofungin group and already switched to oral therapy).
- v. On Day 15, subjects may receive either IV CD101 (if in a CD101 group and not switched to oral therapy), if needed; IV caspofungin (if in caspofungin group and not switched to oral therapy), if needed; IV CD101 plus oral placebo (if in a CD101 group and already switched to oral therapy), if needed; IV placebo plus oral fluconazole (if in caspofungin group and already switched to oral therapy), if needed; or no treatment.
- w. On Days 16-21, subjects may receive either IV caspofungin (if in caspofungin group), if needed; IV placebo (if in a CD101 group), if needed; oral fluconazole (caspofungin group) if already switched and needed; oral placebo (CD101 groups) if already switched and needed; or no treatment.
- x. On Day 22, subjects with IC (with or without candidemia) may receive either IV CD101 (if in a CD101 group and not switched to oral therapy), if needed; IV caspofungin (if in caspofungin group and not switched to oral therapy), if needed; IV CD101 plus oral placebo (if in a CD101 group and already switched to oral therapy), if needed; IV placebo plus oral fluconazole (if in caspofungin group and already switched to oral therapy), if needed; or no treatment.
- y. On Days 23-28, subjects may receive either IV caspofungin (if in caspofungin group), if needed; IV placebo (if in a CD101 group), if needed; oral fluconazole (caspofungin group) if already switched and needed; oral placebo (CD101 groups) if already switched and needed; or no treatment
- z. Oral step-down therapy will be fluconazole (a loading dose of 800 mg [4 capsules] on the first day followed by 400 mg [2 capsules]/day thereafter) in the caspofungin group and oral placebo (4 capsules on the first day followed by 2 capsules/day thereafter) in the CD101 groups.
- aa. Record all systemic antifungal therapy administered within 4 weeks and all non-antifungal therapy administered within 1 week prior to randomization Record concomitant antimicrobial agents, including all antifungal agents at each study visit.

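### SAP Section 5.2.1 has no IV-therapy band above 21 days, although subjects with invasive candidiasis may receive IV study drug up to Day 28

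*SAP*

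**What the plan says.** SAP Section 5.2.1 describes three summaries of treatment duration in one paragraph.

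- Total duration, IV and oral together, is banded with an open top category: the list starts at 1–7 and 8–14 days and ends with "15-21 and >21 days of exposure (IV and oral) as defined above will be presented".
- Duration by route is summarized without bands: "Descriptive statistics will also be provided separately for the duration of IV therapy and the duration of oral therapy".
- IV duration is then banded: "The number and percentage of subjects with 1-3, 4-7, 8-14 and 15-21 days of IV therapy will be presented".

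Section 1.2.1 gives the permitted length of IV caspofungin: "up to a maximum of 21 days for subjects with candidemia only or up to a maximum of 28 days for subjects with IC". Table 1-1 in Section 1.2.5 carries this into the schedule. Footnote x allows IV dosing on Day 22 for subjects with IC. Footnote y covers the days after that: "On Days 23-28, subjects may receive either IV caspofungin (if in caspofungin group), if needed; IV placebo (if in a CD101 group), if needed".

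**The concern.** The four IV bands fit the 21-day limit for candidemia alone and do not reach the 28-day limit for IC. A subject with IC who stays on IV therapy past Day 21 follows the plan and still has no row in the IV table.

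The same subject does have a row for total exposure, because that list includes >21. The SAP gives no reason for ending one list at 21 days and leaving the other open.

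At stake is the completeness of a descriptive safety-exposure table. Safety and tolerability are a primary objective (Section 1.1.2), and the longest IV exposures are the ones for which the banded rows have no place.

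**Working it through.** No sample-size or power figure is involved. The check assigns each permitted IV duration to the stated bands.

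**Inputs**

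- IV bands (Section 5.2.1): 1–3, 4–7, 8–14, 15–21 days.
- Total-exposure bands (Section 5.2.1): 1–7, 8–14, 15–21, >21 days.
- Maximum IV caspofungin (Section 1.2.1): 21 days for candidemia only, 28 days for IC.
- IV dosing on Day 22 and on Days 23–28 for IC (Table 1-1, footnotes x and y).

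**Step 1: durations covered.** The IV bands hold 3 + 4 + 7 + 7 = 21 consecutive durations, 1 to 21 days. For candidemia only (maximum 21) nothing is uncovered. For IC (maximum 28), 28 − 21 = 7 durations have no band: 22, 23, 24, 25, 26, 27 and 28 days. The total-exposure bands leave none of the 28 uncovered.

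**Step 2: one permitted case.** A caspofungin subject with IC receives daily IV drug from Day 1 to Day 25 with no oral step-down. Duration by the section's formula is last day − first day + 1 = 25 − 1 + 1 = 25 days, and the number of IV dosing days is also 25. Total-exposure band: >21. IV band: none. Section 5.2.1 does not say whether IV placebo days in the CD101 groups count as IV therapy, but the gap does not depend on that, because this subject receives active IV drug throughout.

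**Step 3: effect on the percentages.** With k subjects above 21 IV days in a group of N, the four bands add to 100 × (N − k)/N percent. This is 100% only if k = 0. The SAP gives no expected k, so no size in subjects can be stated.

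**Step 4: tables affected.** Under Sections 5.2 and 5.2.1 these are:

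- the Safety-population tables for Part A, Part B and the two parts combined;
- the Safety subgroup tables by region, hepatic insufficiency, renal function status and renal disease;
- the mITT table, which is produced only for Parts A and B combined.

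**Step 5: the remedy.** With a fifth band of >21, every duration from 1 to 28 days falls in exactly one band. Being open-ended, it would also hold a subject who ran to Day 29 or 30 within the ±2 days that Section 1.2.5 attaches to Day 28.

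**The case against.** The strongest reply is that little information is lost. The sentence just before the IV bands promises descriptive statistics for IV duration, and Section 3.2 defines these to include the number of subjects, mean, median, SD, minimum and maximum. Subjects with 22 to 28 IV days are in that summary, and the maximum would show that they exist. Their doses are in the by-subject IV listing. The missing count can also be recovered by subtracting the four bands from the group total, if the full group is the denominator. All of this stands, and it keeps the point at the lowest level.

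It does not remove the point. The band list is a stated rule, no other section adds a higher IV band, and a reader should not have to find the longest IV exposures by subtraction.

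Two stronger readings are tempting, and the SAP supports neither. A reader might infer that these subjects disappear from IV-exposure reporting altogether; they are missing from the banded rows only. A reader might also infer that a sizeable share of a group is lost. Seven of 28 counts durations, not subjects. Only IC subjects can exceed 21 days, and if none stays on IV that long the bands add to 100%. Footnote d of Table 1-1, which mentions 26 or more days of therapy, does not help, because it does not say that the therapy is IV; the total-exposure bands already cover such subjects.

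**Conclusion.** The point holds as a minor error in how the table is specified. Followed exactly, Section 5.2.1 leaves any subject with 22 to 28 days of IV therapy out of every IV band, although Section 1.2.1 and Table 1-1 permit that length of IV treatment in IC. The conclusion rests only on the stated bands and the stated IV limits. The shortfall in the percentages arises only if at least one subject with IC remains on IV therapy beyond Day 21, and the SAP gives no basis for estimating how many will. Only descriptive exposure tables are touched: no endpoint, analysis population, confidence interval or comparison between groups changes.

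**What to change.** In Section 5.2.1, make the IV-therapy bands 1–3, 4–7, 8–14, 15–21 and >21 days, so that the top category matches the total-exposure bands in the same paragraph. Carry the extra row into the Safety, Safety subgroup and combined mITT exposure tables. The cost is one row per table and a small text change before database lock. No new data are needed, since all IV doses are already to be listed by subject.
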